# 1 SYNOPSIS

Title of Study	A Phase 3, Multicenter, Open-Label Study to Assess the Long-Term Safety of REL-1017 as a Treatment of Major Depressive Disorder (RELIANCE-OLS)
Sponsor	Relmada Therapeutics, Inc. (Relmada)
Investigators/Study Sites	Approximately [REDACTED] planned in the United States
Phase of Development	3

Objectives	Endpoints
Primary	
To evaluate the long-term safety and tolerability of REL-1017 as adjunctive treatment to an approved antidepressant therapy (ADT) and as a monotherapy.	
 
• Treatment-emergent adverse events (TEAEs)
 

Secondary	
To evaluate the long-term safety of REL-1017 as adjunctive treatment to an approved ADT and as a monotherapy.	
 
• Evaluate the effects on the electrocardiogram (ECG), including heart rate, pulse rate (PR), QRS, and QT interval with Fridericia's correction (QTcF) intervals
 
• Vital signs and weight
 
• Physical examination
 
• Clinical laboratory parameters (chemistry, hematology, and urinalysis)
 
• Columbia-Suicide Severity Rating Scale (C-SSRS)
 
• Clinician-Administered Dissociative States Scale (CADSS)
 
• [REDACTED]
 

Exploratory	
To evaluate the impact and long-term durability of REL-1017 as an adjunctive treatment to an approved ADT and as a monotherapy over a 1-year period on depression, [REDACTED] [REDACTED] [REDACTED] [REDACTED]	
 
• The Montgomery-Åsberg Depression scale (MADRS10) 
 
○ Absolute value and change from Baseline of MADRS10 total score
 
○ Remission rate (total score <math>\leq 10</math>)
 
○ Response rate (improvement <math>\geq 50\%</math> compared with total Baseline score)
 
○ Time course of changes from Baseline
 
 
 
• Clinical Global Impression of Severity (CGI-S) score
 
• Hamilton Anxiety Rating Scale (HAM-A) total score
 
• Symptoms of Depression Questionnaire (SDQ) total score
 
• Sheehan Disability Scale (SDS) domain score
 
• Clinical Global Impression of Improvement (CGI-I) score
 
• [REDACTED]
 
• [REDACTED]
 
• [REDACTED]
 
• [REDACTED]
 

- A double-barrier protection method (e.g., condom, sponge, or vaginal diaphragm with spermicide cream, foam, or gel)

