
Statistical Data Analysis
	
Study analysis populations, defined as follows:
 
Screened/Enrolled Set: The Screened/Enrolled Set will include all participants who signed an informed consent.
 
Full Analysis Set (FAS): All participants who received at least 1 dose of study drug in the OLS and had at least 1 post-Baseline efficacy assessment, irrespective of any deviation from the protocol or premature discontinuation. The FAS will be used for analysis of efficacy.
 
Safety Set: All participants who received at least 1 dose of study drug in the OLS. This population will be used for the analysis of safety.
 
Safety data analysis
 
Descriptive statistics of the safety and efficacy of the participants in the OLS will be presented based on the prior double-blind treatment groups: Double-blind placebo, double-blind REL-1017, de novo. In general, the Baseline for each assessment will be the last value collected prior to the first open-label dose.
 
Summaries of efficacy results will be presented for the FAS, and summaries of safety results will be presented for the Safety Set; all will be summarized by the treatment groups “REL-1017 in double-blind study,” “placebo in double-blind study,” “de novo,” “pooled placebo and de novo,” and “overall”.
 
Continuous safety and tolerability assessments (e.g., vital signs, weight, BMI, body temperature, ECG parameters, and laboratory parameters) will be summarized using descriptive statistics for values for each visit, and additionally for change from Baseline of OLS.
 
The time course of absolute values and change from Baseline will be presented in descriptive statistics and figures.
 
Categorical safety data (e.g., categorical laboratory parameters, ECG overall evaluation, QT/QTcF categories) and central tendency effects will be presented by number and percentage of participants in the respective category for each visit.
 
The number and percentage of participants with TEAEs, serious adverse events (SAEs), AEs associated with discontinuation, and TEAEs by severity and relationship to study treatment will be summarized by system

---	---

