	
organ class and preferred term, using the Common Terminology Criteria for Adverse Events (CTCAE) v5.0.
 
All summaries of TEAEs will be provided for the TEAEs in OLS (i.e., AEs that started or worsened in severity after first dose in the OLS).
 
Comorbidities and comedications will be summarized in count and frequency tables.
 
Exploratory Efficacy variables
 
Continuous efficacy variables will be reported using descriptive statistics for values for each visit, and additionally for change from Baseline of OLS. The time course of absolute values and change from Baseline will be presented in figures.
 
Categorical efficacy data will be presented by number and percentage of participants in the respective category for each visit.

--	--

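### TEAEs, the primary endpoint of a long-term safety study, are summarised only as crude percentages of everyone dosed, with no measure of exposure or time to onset

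*Combined protocol and SAP*

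**What the plan says.** All references are to section 1, Synopsis.

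- **Objective and endpoint.** The primary objective is "To evaluate the long-term safety and tolerability of REL-1017 as adjunctive treatment to an approved antidepressant therapy" and as monotherapy. The one endpoint listed against it is TEAEs.
- **Summary measure.** Under Safety data analysis, the plan is to summarise "The number and percentage of participants with TEAEs, serious adverse events (SAEs), AEs associated with discontinuation", and TEAEs by severity and relationship, by system organ class and preferred term.
- **Counting rule.** TEAEs are "AEs that started or worsened in severity after first dose in the OLS". This fixes when counting starts but says nothing about each participant's time at risk.
- **Denominator.** The Safety Set is all participants who "received at least 1 dose of study drug in the OLS. This population will be used for the analysis of safety".
- **Columns.** There are five: prior double-blind REL-1017, prior double-blind placebo, de novo, placebo and de novo pooled, and overall.
- **Other safety data.** Continuous measures are summarised by visit, and "The time course of absolute values and change from Baseline will be presented in descriptive statistics and figures". Categorical laboratory and ECG data are also shown by visit.
- **Early stopping.** It is foreseen: the Full Analysis Set keeps participants "irrespective of any deviation from the protocol or premature discontinuation", and adverse events associated with discontinuation are tabulated.
- **Duration.** The only duration in the text available is in the exploratory objective: "as an adjunctive treatment to an approved ADT and as a monotherapy over a 1-year period on depression".

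**The concern.** In the planned tables a participant observed for one week counts the same in the denominator as one observed for a year. If people leave before an event they would otherwise have had, the percentage drops although the risk has not changed. The effect is greatest for events spread over the year or starting late, which are the events a long-term study is best placed to find.

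Two readings are at stake. First, a low percentage may reflect low risk or short observation, and the table alone cannot separate them. Second, columns with the same risk but different dropout will show different percentages. A smaller point concerns the overall column, which mixes participants first exposed in the OLS with participants already treated with REL-1017 in the double-blind study.

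**Working it through.** **Inputs.** The text available gives no TEAE rate, dropout rate or column size, so there is no plan figure to reproduce. The 1-year horizon comes from the exploratory objective. Everything else below is an assumption.

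**Formula.** With a 1-year dropout proportion *p*, the dropout hazard is d = −ln(1 − p) per year, giving 0.105, 0.357 and 0.693 for 10%, 30% and 50%. With event hazard *l* in each interval and dropout independent of events:

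crude proportion = Σ S(start) × l/(l + d) × [1 − exp(−(l + d) × length)],

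where S(start) is the proportion still event-free and on study when the interval begins.

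**Two event patterns.**

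1. *Front-loaded*: 20% risk in month 1, then 10% over months 2–12. Hazards are l₁ = −ln(0.8) × 12 = 2.678 and l₂ = −ln(0.9) × 12/11 = 0.115 per year. The 1-year risk is 1 − 0.8 × 0.9 = 28.0%.
2. *Constant*: l = 0.5 per year. The 1-year risk is 1 − exp(−0.5) = 39.3%.

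Example for pattern 2 at 30% dropout: 0.5/0.857 × [1 − exp(−0.857)] = 0.5836 × 0.5754 = 33.6%.

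| Dropout | Front-loaded crude (true 28.0%) | Constant crude (true 39.3%) |
|---|---|---|
| 10% | 27.5% | 37.5% |
| 30% | 26.4% | 33.6% |
| 50% | 25.1% | 29.2% |

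**Column comparison.** Two columns with identical risk but 30% and 50% dropout differ by 1.3 points in pattern 1 and 4.4 points in pattern 2. With equal dropout the gap is zero.

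**Early-onset limit.** If every event falls in month 1, the shortfall nearly vanishes: a true 10% shows as 9.9% at 30% dropout and 9.7% at 50%. With constant hazard the same 10% shows as 8.4% and 7.3%.

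**Why rates by interval.** In pattern 1 the whole-period rate of first events per person-year itself moves with dropout (0.375, 0.405 and 0.446 at 10%, 30% and 50%), because early, high-risk time gains weight. The interval rates stay at 2.678 and 0.115.

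**Informative dropout.** Suppose half the participants have three times the hazard of both events and dropout, calibrated to the same 1-year risk and 30% dropout. The Kaplan-Meier cumulative incidence is then also low, but nearer the truth: 27.5% against crude 26.1% (true 28.0%) in pattern 1, and 37.9% against crude 32.7% (true 39.3%) in pattern 2.

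**Precision.** At 30% dropout, the asymptotic Greenwood 95% half-width at Month 12 is 9.2 points (pattern 1) and 10.6 points (pattern 2) with 100 per column, and 5.3 and 6.1 points with 300. The proportion still event-free and on study at Month 12 is 50% and 42%.

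**Overall column.** In pattern 1 at 30% dropout, first-exposed participants show 26.4%. Let previously treated participants be 10% to 30% of the Safety Set. The overall figure is then:

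- 24.6% down to 21.2% if they carry only the later hazard (their own crude figure is 9.2%; for example 0.1 × 9.16 + 0.9 × 26.36 = 24.6);
- 26.4% if their risk is equal;
- 27.4% up to 29.5% if their hazard is 1.5 times higher (their own crude figure is 36.7%).

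The direction is therefore not known in advance.

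**The case against.** The strongest objection is that this rests on an incomplete synopsis. Exposure summaries and onset-interval tables usually sit in the full statistical section, so their absence here is weak evidence that the plan lacks them. That stands, and the recommendation is conditional on it.

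Second, number and percentage by system organ class and preferred term is a standard and valid description of events while observed, and the plan never names 1-year risk as the TEAE target. This also stands. The point is what is missing beside the percentage, given an objective that says long-term.

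Third, the comparability argument is weak in practice. The analysis is descriptive, differential dropout is not shown, and the illustrated gaps are within sampling error: the 95% half-width for a difference in crude percentages is about 12 to 13 points at 100 per column and about 7 at 300. That is correct. The shortfall within each column, however, is systematic and does not shrink with sample size.

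Fourth, someone who stops because of a TEAE is already counted for that event, so that part of dropout causes no shortfall for it. True, but dropout for other reasons still does.

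Fifth, Kaplan-Meier is itself biased when dropout is informative. It is, but in the case worked here by less than the crude figure.

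Finally, the column labels already disclose what the overall column contains. That makes the footnote minor, and it would not justify a comment alone.

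**Conclusion.** The concern holds for the text available. The sole primary endpoint is given no time dimension, while other safety data in the same section are. Under the assumptions used, the crude percentage understates the 1-year risk by 0.5 to 2.9 points when risk is front-loaded and by 1.8 to 10.1 points when hazard is constant, for dropout of 10% to 50%. The true size is unknown, and it is small for early-onset events. No planned test is affected, so this is a worthwhile and inexpensive improvement to reporting. Confidence is medium, because fuller sections may already cover it.

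**What to change.** Keep the planned counts and percentages. Add, by column:

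- exposure duration and total person-years;
- TEAEs, SAEs and adverse events associated with discontinuation by onset interval (for example month 1, months 2–3, 4–6 and 7–12), with exposure-adjusted rates per interval;
- cumulative incidence of first TEAE with 95% confidence intervals at a few fixed times, including Month 12. State that it assumes non-informative censoring and that this is doubtful where adverse events cause discontinuation.

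Footnote the overall column as mixing participants first exposed in the OLS with participants already treated with REL-1017, so that it may lie above or below first-exposure incidence. Refer readers to the existing column that pools placebo and de novo participants.

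The cost is SAP wording, a few tables and one footnote, using adverse event onset dates and last-dose or last-contact dates. Late estimates will be imprecise and should be read with their intervals. If other sections already specify the time-based tables, only the footnote is needed.
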